6.2. Study Period (for both Treatment Period I and Treatment Period II)

6.2.1. Baseline/Visit 1 (Study Day 1, Week 0)

This visit can occur as soon as the laboratory results from the screening visit are available provided all other eligibility requirements have been met. The following procedures and assessments should be made before randomization and subject injection:

- Verify trial eligibility by checking and documenting inclusion and exclusion criteria ([Sections 4.1 and 4.2](#));
- Measure and record vital signs: heart rate, temperature, respiratory rate and blood pressure ([Section 7.2.2](#));
- Measure and record body weight;
- Obtain and record ongoing medications and instruct the subject on the use of concomitant medications ([Section 5.8](#));
- Conduct brief/limited physical exam ([Section 7.2.4](#));
- Inquire for and record adverse events;
- Conduct contraception check ([Section 4.4.1](#)).
- Collect specimens for laboratory exams:
 - Urine for pregnancy test (WOCBP).
- Randomization:
 - Access IRT to obtain randomization number for the subject.
- Questionnaire Administration:
 - Provide DCOA1 questionnaire and train Subject/Caregiver Dyad on completion;
 - Subject/Caregiver Dyad completes DCOA1 questionnaire;
 - Subject/Caregiver Dyad completes PGIS-IDA question;
 - Clinical Site Staff completes DYAD Questionnaire.
- Drug dispensation and dosing:
 - Dispense investigational product based on IRT randomization code and container number on the container;

- Instruct subject on injection;
- Subject will inject study treatment;
- Instruct and provide subjects with the subject diary corresponding to the treatment they are assigned.
- Assessment during and after subject injection:
 - Injection site assessment;
 - Inquire for and record adverse events;
 - Inquire for and record injection device complaints;
 - Inform subject/caregiver of date of next visit and required dates of administration of study drug.

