3. STUDY DESIGN

The study is a randomized, open-label, multi-center, 2-period crossover in children 3 to <18 years of age with GHD. The planned study duration is 24 weeks with a screening period of up to 30 days and a follow-up phone call four weeks after the last clinic visit. Approximately 90 children with GHD who have been stable on treatment with daily Genotropin[®] for a minimum of 3 months will be enrolled. Subjects will be randomized to one of two sequences, either 12 weeks of continued treatment with daily Genotropin[®] followed by 12 weeks of treatment with weekly somatrogon, or 12 weeks of treatment with weekly somatrogon followed by 12 weeks of treatment with daily Genotropin[®] (see Figure 2 below). There will be no treatment wash-out period since these subjects must take growth hormone continually. Subjects will have study visits at Baseline, Weeks 6, 12, 18, and 24. Subjects will also be followed up by phone 8-12 days after each treatment period begins (Week 1 and Week 13). Subjects and caregivers (as a Dyad) will complete the DCOA questionnaires at baseline and at the end of each 12 week treatment period (DCOA 1 at baseline and after Period I and Period II; DCOA 2 after Period II). Subjects and caregivers will also complete the PGIS-IDA at baseline and after Period I and Period II. [Appendix 5](#) describes which sub-group (subject and/or caregiver) completes which part of the questionnaire and at which time point. All subjects/caregivers will receive a follow up phone call at Week 28.

Figure 2. Study Design

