5.1. Allocation to Treatment

The investigator's knowledge of the treatment should not influence the decision to enroll a particular subject or affect the order in which subjects are enrolled.

Allocation of subjects to treatment groups will proceed through the use of an interactive response technology (IRT) (interactive Web-based response system [IWRS]). The IRT system will provide a confirmation report containing the subject number, randomization number, and dispensable units (DU) or container numbers assigned. The confirmation report must be stored in the site's files.

The study-specific IRT reference manual will provide the contact information and further details on the use of the IRT system.

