### **3.4. Baseline Variables**

No variables require specific definitions for baseline.

As this is a cross-over study with no washout period after the end of treatment period I and before the start of treatment period II, baseline is calculated as the last pre-dose assessment prior to administering the study drug at Baseline/Visit 1 (Study Day 1 Week 0).

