### 6.4. Subset Analyses

Additional analyses for the primary endpoint using the FAS population may be undertaken if adequate number of subjects are available for each analyses. The following sub-analyses on Life Interference may be considered exploratory for this purpose and support the evidence for the potential advantage of weekly somatrogon in comparison to daily administration of Genotropin® as it is expected to result in increased adherence and better acceptance of weekly dosing:

- Aged <8 years vs  $\geq 8$  years;
- Aged 3 – 11 vs 12 - <18 years;

- Caregiver injection vs self-injection;
- Burdened vs not burdened, defined by the response at baseline to the question “During the past 4 weeks, how often were you bothered by growth hormone injections?” (question 3 from Patient Life Interference Section I questionnaire), as follows:
  - Not burdened: subjects experiencing little to no burden (never, rarely);
  - Burdened: subjects experiencing at least moderate burden (sometimes, often, always).

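### Protocol 6.2.1 contradicts itself on whether the baseline burden questionnaires precede randomisation, so in this open-label trial they can be answered with the sequence known

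*Protocol*

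**What the plan says.** Protocol 6.2.1 introduces the Visit 1 list with "The following procedures and assessments should be made before randomization and subject injection". The list then runs: eligibility check and examinations; randomisation ("Access IRT to obtain randomization number for the subject"); questionnaires ("Subject/Caregiver Dyad completes DCOA1 questionnaire", "Subject/Caregiver Dyad completes PGIS-IDA question", and the staff-completed DYAD form); dispensing, instruction, injection and diary; and checks during and after the injection.

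On masking, Protocol 3 states: "The study is a randomized, open-label, multi-center, 2-period crossover in children 3 to <18 years of age with GHD". On what the site learns at randomisation, Protocol 5.1 states: "The IRT system will provide a confirmation report containing the subject number, randomization number, and dispensable units (DU) or container numbers assigned".

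SAP 3.4 ties baseline to dosing and not to randomisation: "baseline is calculated as the last pre-dose assessment prior to administering the study drug at Baseline/Visit 1". SAP 6.4 then uses a baseline answer to form a subset: "Burdened vs not burdened, defined by the response at baseline to the question" of how often the injections were a bother over the preceding four weeks. Never and rarely count as not burdened; sometimes, often and always count as burdened.

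**The concern.** The lead-in and the list cannot both hold. A list that itself contains randomisation, dosing and post-dose checks cannot all be done before randomisation. A site working down the page would randomise first and question the dyad second, and the SAP would accept the result as a valid baseline.

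The items are subjective. A dyad that knows it is staying on daily injections for 12 weeks, or is about to change to weekly ones, might rate its present burden differently. If so, a one-category move between rarely and sometimes changes the subset to which the dyad belongs. A classifier recorded before randomisation cannot depend on sequence; one recorded afterwards can. SAP 6.4 intends these subset analyses as supporting evidence for the weekly schedule. Baseline Life Interference (SAP 6.1.1.1) and baseline PGIS-IDA (SAP 6.2.3) are also summarised.

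**Working it through.** **Does any other text fix the order?**

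| Source | What it settles |
|---|---|
| Protocol 6.2.1, lead-in | Assessments before randomisation and injection |
| Protocol 6.2.1, list | Randomisation printed above the questionnaires; dispensing below them |
| Protocol 5.4 | Assessments and randomisation both before the first dose; neither ordered before the other |
| Schedule of Activities | All at Visit 1; no order within the visit |
| Protocol 5.1 | The site receives randomisation and container numbers; silent on when the dyad is told |
| SAP 3.4 | Baseline must precede the dose, not randomisation |

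No text requires the questionnaires to come first, and none withholds the sequence until they are complete.

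**Is the primary analysis touched?** SAP 6.1.1.1 uses the Week 12 and Week 24 scores. The model in SAP 5.2.2 has sequence, period and treatment as fixed effects and no baseline covariate. A change in baseline answers therefore cannot enter the estimate.

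**Does the sample size depend on it?** The inputs from Protocol 9.1 are difference 0.45, SD 1, correlation 0.3, two-sided alpha 0.05 and power 90%.
- SD of the paired difference = sqrt(2 × (1 − 0.3)) × 1 = 1.183.
- Normal approximation: ((1.960 + 1.282) × 1.183 / 0.45)² = 72.6, so 73.
- Exact paired t: n = 75, power 0.9016, which reproduces the plan's 75.
- 75 × 1.20 = 90, at which power is 0.946.

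No baseline quantity appears, so reordering the visit changes none of these figures.

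**What could happen to the subset?** The documents do not give the size of a reporting shift, so the following is purely illustrative. Assumptions: 90 subjects, 45 per sequence; normal scores with SD 1 and correlation 0.3; burdened means above the average; baseline answers raised by 0, 0.2 or 0.45 SD in the daily-first sequence only; 2,000 simulated trials.
- The share classed as burdened in the shifted sequence is Φ(shift): Φ(0) = 50%, Φ(0.2) = 58%, Φ(0.45) = 67%. The simulated shares were 0.501, 0.579 and 0.675. The other sequence stays at 0.499.
- The primary estimate is −0.455 at every shift.
- If the treatment effect does not vary with baseline burden, the subset estimates stay between −0.454 and −0.456.
- If the effect is assumed to be −0.45 − 0.3 × (true baseline in SD), the estimates move as below.

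| Shift (SD) | Burdened | Not burdened |
|---|---|---|
| 0 | −0.694 | −0.215 |
| 0.2 | −0.676 | −0.195 |
| 0.45 | −0.655 | −0.168 |

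The largest movements are 0.694 − 0.655 = 0.039 and 0.215 − 0.168 = 0.047. Membership becomes visibly unbalanced by sequence; the within-subset contrasts change little.

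**The case against.** The strongest reply is that this is loose drafting. The lead-in signals an intention to assess before randomisation, and nothing says that printed order is chronological. The Schedule of Activities prints the injection row above DCOA 1, although 6.2.1 places DCOA 1 before dosing. Dispensing, injection instruction and the treatment-specific diary all come after the questionnaires, so the dyad may not know its sequence when it answers. Every dyad is due to receive both schedules, so knowing the sequence reveals only their order. The bother item and the PGIS-IDA ask about the past four weeks, which have already been lived.

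Much of this stands. A reader might infer that the plan deliberately measures baseline after allocation, or that dyads are told their sequence first. The documents permit the second but state neither. A reader might also infer that the subset contrast loses the protection of randomisation, as it could in a parallel-group trial. Here each subject is compared with itself, sequence and period are in the model, and the illustration shows no movement without effect modification. What can depend on sequence is membership, which is a narrower claim.

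The reply does not remove the contradiction, and it points to no sentence that rules out a baseline taken after disclosure.

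**Conclusion.** The point holds as an internal contradiction with limited consequences. Protocol 6.2.1 and SAP 3.4 together allow the baseline burden items to be answered after the sequence is known. What is exposed is membership of one optional, exploratory subset and the descriptive baseline summaries of burden.

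It would be wrong to infer any threat to the primary result: the Week 12/Week 24 contrast, the 75 and 90 subjects and the power do not involve baseline. It would also be wrong to put a number on the dyads reclassified. The documents do not say how many lie near the rarely/sometimes cut, how many would move, or whether the direction would differ by sequence. The 0 to 0.45 SD shifts and the 0.3 effect modification above are assumptions chosen to show the mechanism, not estimates. The change is worth making because it costs little, agrees with the protocol's own lead-in, and removes a possible source of bias from a subjective classifier.

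**What to change.** 1. In Protocol 6.2.1, move the questionnaire block (DCOA 1, PGIS-IDA, DYAD) above the IRT randomisation step, and limit the lead-in to the steps that precede randomisation.
2. In SAP 3.4, for visits run in that order, define questionnaire baseline as the last assessment before randomisation. Do not make this change alone. DCOA 1 is first given at Visit 1, so a dyad assessed in the printed order would be left with no questionnaire baseline.
3. For dyads already assessed, keep the pre-dose questionnaire as baseline. Flag from ePRO and IRT time records, if available, whether it followed randomisation, and interpret the burdened/not-burdened subset accordingly.

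The reorder adds no procedure, visit or subject, but it is a protocol change and needs ethics approval under Protocol 12.1. SAP version 3 already refers to questionnaires completed by an alternative method because of COVID-19, which suggests that collection was under way. For completed visits only the third step can help; it needs a data check and a sentence in the report.

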6.2.2. Visit 2 (Study Day 8 + 4 days, Week 1)

Visit 2 is a follow-up phone call that will occur 8-12 days following Visit 1. The following assessments should be made:

- Obtain and record ongoing medications and instruct the subject on the use of concomitant medications ([Section 5.8](#));
- Injection site assessment;
- Inquire for and record adverse events;
- Inquire for and record injection device complaints;
- Inform subject/caregiver of date of next visit and that subject should bring all used study medication containers, used cartridges and/or injection devices, and subject diary to that visit.

6.2.3. Visit 3 (Study Day 42 ±4 days, Week 6)

Visit 3 is at the clinical site and the following procedures and assessments should be made:

- Obtain and record ongoing medications and instruct the subject on the use of concomitant medications ([Section 5.8](#));
- Measure and record vital signs: heart rate, temperature, respiratory rate and blood pressure ([Section 7.2.2](#));
- Conduct brief/limited physical exam ([Section 7.2.4](#));

- Conduct contraception check ([Section 4.4.1](#));
- Collect all used study medication containers (drug accountability);
- Collect all used cartridges and/or injection devices (drug accountability);
- Review and collect subject diary and instruct/provide subject with new subject diary for the remainder of treatment period;
- Injection site assessment;
- Inquire for and record adverse events;
- Inquire for and record injection device complaints;
- Drug Dispensation:
 - Dispense Genotropin to subjects in Sequence 1.
- Inform subject/caregiver of date of next visit and that subject should bring all used and unused study medication containers, used and unused cartridges and/or injection devices, and subject diary to that visit;
- Inform subjects that regarding the next visit (Visit 4):
 - Subjects that will be switching from Genotropin[®] to somatrogon should administer their final injection of Genotropin[®] 36 hours (± 24 hours) prior to Visit 4;
 - Subjects that will be switching from somatrogon to Genotropin[®] should administer their final injection of somatrogon 7 days (± 72 hours) prior to Visit 4.

6.2.4. Visit 4 (Study Day 84 + 4 days, Week 12) – Crossover/Treatment Change

Visit 4 is at the clinical site and is where subjects will be switched based on their assigned sequence from Genotropin[®] to somatrogon or from somatrogon to Genotropin[®].

Subjects who discontinue study treatment prior to beginning Period II of the study will be asked to complete the assessments and procedures outlined in Visit 4 (except for drug dispensation, and dosing and assessments during and after subject injection).

The following procedures and assessments should be made before subject self-injection:

- Obtain and record ongoing medications and instruct the subject on the use of concomitant medications ([Section 5.8](#));

- Measure and record vital signs: heart rate, temperature, respiratory rate and blood pressure ([Section 7.2.2](#));
- Conduct brief/limited physical exam ([Section 7.2.4](#));
- Conduct contraception check ([Section 4.4.1](#));
- Collect all used and unused study medication containers (drug accountability);
- Collect all used and unused cartridges and/or injection devices (drug accountability);
- Review and collect subject diary;
- Injection site assessment;
- Inquire for and record adverse events;
- Inquire for and record injection device complaints;
- Collect fasting (10 hours) specimens for laboratory exams:
 - Blood for fasting lipid profile, hematology with differential, blood chemistry, liver function tests, FT4, IGF-I, IGF-I SDS, hemoglobin A1c, somatrogon level and anti-somatrogon Ab (and neutralizing Ab) (only for subjects who have been on somatrogon for the previous 12 weeks of treatment), and anti-rhGH Ab (and neutralizing Ab);
 - Urine for urinalysis;
 - Urine for pregnancy test (WOCBP).
- Questionnaire Administration:
 - Provide DCOA1 questionnaire and train Subject/Caregiver Dyad on completion;
 - Subject/Caregiver Dyad completes DCOA1 questionnaire;
 - Subject/Caregiver Dyad completes PGIS-IDA question;
 - Clinical Site Staff completes DYAD Questionnaire.
- Drug dispensation and dosing:
 - Confirm for subjects switching from Genotropin[®] to somatrogon that it has been 36 hours (± 24 hours) since their most recent injection of Genotropin[®] relative to this visit;

- Confirm for subjects switching from somatrogon to Genotropin[®] that it has been 7 days (± 72 hours) since their most recent injection of somatrogon relative to this visit;
- Dispense new study treatment based on randomization;
- Instruct subject on injection;
- Subject will inject study treatment;
- Instruct/provide subjects with a new subject diary corresponding to the treatment they are switching to.
- Assessments during and after subject injection:
 - Injection site assessment;
 - Inquire for and record adverse events;
 - Inquire for and record injection device complaints;
 - Inform subject/caregiver of date of next visit and required dates of administration of study drug.

6.2.5. Visit 5 (Study Day 92 + 4 days, Week 13)

Visit 5 is a follow-up phone call that will occur 7-11 days following Visit 4. The following assessments should be made:

- Obtain and record ongoing medications and instruct the subject on the use of concomitant medications ([Section 5.8](#));
- Injection site assessment;
- Inquire for and record adverse events;
- Inquire for and record injection device complaints;
- Inform subject/caregiver of date of next visit and that subject should bring all used study medication containers, used cartridges and/or injection devices, and subject diary to that visit.

6.2.6. Visit 6 (Study Day 126 \pm 4 days, Week 18)

Visit 6 is at the clinical site and the following procedures and assessments should be made:

- Obtain and record ongoing medications and instruct the subject on the use of concomitant medications ([Section 5.8](#));

- Measure and record vital signs: heart rate, temperature, respiratory rate and blood pressure ([Section 7.2.2](#));
- Conduct brief/limited physical exam ([Section 7.2.4](#));
- Conduct contraception check ([Section 4.4.1](#));
- Collect all used study medication containers (drug accountability);
- Collect all used cartridges and/or injection devices (drug accountability);
- Review and collect subject diary and instruct/provide subject with new subject diary for the remainder of treatment period;
- Injection site assessment;
- Inquire for and record adverse events;
- Inquire for and record injection device complaints;
- Drug Dispensation:
 - Dispense Genotropin to subjects in Sequence 2.
- Inform subject/caregiver of date of next visit and that subject should bring all used and unused study medication containers, used and unused cartridges and/or injection devices, and subject diary to that visit.

6.2.7. Visit 7 (Study Day 168 ±4 days, Week 24) – End of Study Visit

Visit 7 is at the clinical site and is the last visit of the study prior to follow up phone contact.

Subjects who discontinue treatment during Period II but before the end of study visit will be asked to complete the assessments and procedures outlined in Visit 7. The following procedures and assessments should be made:

- Obtain and record ongoing medications;
- Measure and record vital signs: heart rate, temperature, respiratory rate and blood pressure ([Section 7.2.2](#));
- Conduct brief/limited physical exam ([Section 7.2.4](#));
- Conduct contraception check ([Section 4.4.1](#));
- Collect all used and unused study medication containers (drug accountability);

- Collect all used and unused cartridges and/or injection devices (drug accountability);
- Review and collect subject diary;
- Inquire for and record injection site reactions;
- Inquire for and record adverse events;
- Collect fasting (10 hours) specimens for laboratory exams:
 - Blood for fasting lipid profile, hematology with differential, blood chemistry, liver function tests, FT4, IGF-I, IGF-I SDS, hemoglobin A1c, somatrogon level and anti-somatrogon antibody (and neutralizing Ab) (only for subjects who have been on somatrogon for the previous 12 weeks of treatment), and anti-rhGH antibody (and neutralizing Ab);
 - Urine for urinalysis;
 - Urine for pregnancy test (WOCBP).
- Inquire for and record injection device complaints;
- Injection site assessment;
- Questionnaire Administration:
 - Provide DCOA1 and DCOA2 questionnaires and train Subject/Caregiver Dyad on completion;
 - Subject/Caregiver Dyad completes DCOA1 and DCOA2 questionnaires;
 - Subject/Caregiver Dyad completes PGIS-IDA question;
 - Clinical Site Staff completes DYAD Questionnaire.

6.2.8. Follow-up Contact

Follow-up contact via a phone call will be completed at least 28 calendar days, and up to 35 calendar days after the last administration of the investigational product to capture any potential adverse events (see the [Time Period for Collecting AE/SAE Information](#) section) and to confirm appropriate contraception usage (see the [Contraception](#) section).

6.3. Subject Withdrawal/Early Termination

6.3.1. Withdrawal of Consent

Subjects who request to discontinue study treatment will remain in the study and must continue to be followed for protocol specified follow-up procedures. The only exception to this is when a subject specifically withdraws consent for any further contact with him or her or persons previously authorized by the subject to provide this information. Subjects should

notify the investigator in writing of the decision to withdraw consent from future follow-up, whenever possible. The withdrawal of consent should be explained in detail in the medical records by the investigator, as to whether the withdrawal is only from further receipt of investigational product or also from study procedures and/or post-treatment study follow-up, and entered on the appropriate CRF page.

